5.5.8 Change in Rutherford Category

All subjects from both the ITT and PP populations which have their Rutherford Category measured at the corresponding visit, will be used for calculating the change in Rutherford Category statistics at each visit window. At each time point, the change in Rutherford Category values (post procedures measurement – pre-procedure measurement) will be tabled showing the minimum, maximum, median, mean, and standard error as well as the counts for each outcome.

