4.2. Inclusion Criteria

Potential Subjects must meet all of the following Clinical Inclusion Criteria:

1. Patient is ≥ 18 years old at the time of informed consent signature
2. Patient is willing to give written informed consent
3. Patient has a previously implanted (>30 days) non-covered stent(s) located in the superficial femoral artery
4. Patient has life-style limiting claudication, resting leg pain or minor tissue loss (Rutherford Category 2-5)
5. Patient demonstrates an ABI ≤ 0.9 . If ABI > 0.9 or not measureable, patient is eligible for study if toe-brachial index (TBI) is ≤ 0.5
6. Patient is male, infertile female or female of childbearing potential with a negative beta hCG pregnancy test within 7 days of the index procedure
7. Patient is capable of complying with protocol requirements, including follow-up visits

Potential Subjects must meet all of the following Angiographic Inclusion Criteria:

1. Patient has $\geq 50\%$ in-stent restenosis and/or an occlusion in a previously implanted (>30 days) non-covered stent(s) located in the superficial femoral artery defined as beginning at least 1 cm below the origin of the profunda femoris artery and ending at least 1 cm above the intercondylar notch
2. Patient has a maximum total lesion length of 270 mm, consisting of in-stent and adjacent occlusive disease
3. Patient has a minimum of 1 cm of non-stenosed vessel both proximal and distal to the target lesion(s)
4. Patient has a reference vessel diameter between 4.0 and 6.5 mm
5. The guidewire and delivery system must cross the target lesion(s) intraluminally
6. Patient has a patent popliteal artery ($<50\%$ stenosis) distal to the target vessel
7. Patient has at least 1 patent infrapopliteal runoff vessel ($<50\%$ stenosis) not requiring intervention

CONFIDENTIAL INFORMATION

MD133246 Protocol Template

Revision#: 1

Doc Type: GC

8. Angioplasty balloon can be fully expanded in the target lesion during pre-treatment step

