10.2.8. Change in Rutherford Category

The change in Rutherford Category, measured relative to that obtained pre-procedure, will be assessed at 30 days, 12, 24 and 36 months. The minimum, maximum, median, mean and standard error will be reported as well as the counts for each outcome. All values measured within the defined window will be used in calculation.

CONFIDENTIAL INFORMATION

MD133246 Protocol Template

Revision#: 1

Doc Type: GC

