2.2 Design Summary

This study is a prospective, multicenter, non-randomized single-arm study to evaluate the post-market performance of the GORE® VIABAHN® Endoprosthesis for the treatment of in-stent restenosis in the superficial femoral artery.

A minimum of 15 Clinical Investigative Sites (referred to as “Sites” in the remainder of this document) in the U.S. and a maximum of 5 OUS Sites will participate in this study. A total of 108 Subjects (a minimum of 81 Subjects from the U.S. and a maximum of 27 OUS Subjects) will be enrolled in this study with a limit of 30 Subjects per U.S. Site. A minimum of 20 Subjects (out of the total 108 Subjects) will be enrolled with lesion lengths of 230-270mm. The anticipated accrual period is 24 months assuming an accrual rate is approximately 4.5 Subjects per month.

Patients are to be enrolled into the study provided all inclusion and no exclusion criteria are met as specified in Section 4. Subjects will be evaluated through hospital discharge and will be scheduled for follow-up visits at 30 days and at 12, 24, and 36 months post-treatment. Accounting for the expected period of enrollment, the total estimated duration of the study is 60 months.

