5.2 Analysis Populations

Both of the following populations will be used for analyses of primary and secondary endpoints.

(1) Intent to treat (ITT) – All patients assigned to the study treatment, regardless of whether or not they received it or have any protocol violations.

(2) Per protocol (PP) – A subset of the ITT population consisting of Subjects receiving the study device which meet all inclusion and exclusion criteria and without any major protocol violations.

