5.5.7 Change in ABI

All subjects from both the ITT and PP populations which have their ABI measured at the corresponding visit, will be used for calculating the change in ABI statistics at each visit window. At each time point, the change in ABI values (post procedures measurement – pre-procedure measurement) will be tabled showing at least the minimum, maximum, median, mean, and standard error of the values obtained.

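### Change in Rutherford category and ABI is summarised only in subjects measured at the visit, with no visible rule for study-limb amputation or death, so improvement may be overstated

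*SAP*

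**What the plan says.** SAP 5.5.8 defines who enters the Rutherford summaries: "All subjects from both the ITT and PP populations which have their Rutherford Category measured at the corresponding visit, will be used". SAP 5.5.7 has the matching rule for ABI: "All subjects from both the ITT and PP populations which have their ABI measured at the corresponding visit, will be used". Protocol 10.2.8 puts it in terms of visit windows, "All values measured within the defined window will be used in calculation", and protocol 10.2.7 repeats that sentence for ABI.

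The Rutherford output is the "minimum, maximum, median, mean, and standard error as well as the counts for each outcome". No test is specified for either endpoint, and neither section states a denominator.

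SAP 5.2 defines ITT as "All patients assigned to the study treatment, regardless of whether or not they received it or have any protocol violations". For these two endpoints that set is cut down to the subjects measured at the visit.

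Major amputation (protocol 3.2.1) is removal of the study limb above the metatarsals after a vascular event. It has its own Kaplan-Meier endpoint (protocol 10.2.6, SAP 2.5.6 and 5.5.6). Nothing visible links it to the Rutherford or ABI change. Protocol 5.10 treats death as a withdrawal.

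**The concern.** Whether a Rutherford grade or ankle pressure exists at a visit can depend on the outcome itself. Entry covers Rutherford 2 to 5, so it includes rest pain and minor tissue loss, and limb loss is a possible outcome. Clinical exclusion criterion 10 bars prior major amputation, so any such event in the study limb happens after enrollment.

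If the subject then has no grade, one of the worst limb results in the study leaves the Rutherford table. If a site grades the limb as free of symptoms, that subject counts as improved. If amputation is regarded as the worst outcome, either error favours the device. Running both ITT and PP does not help, because an unmeasured subject is missing from both. The study has a single arm, so there is no control group in which a similar loss could offset it.

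At stake is how the Rutherford mean and outcome counts at 12, 24 and 36 months are read: as the state of the cohort, or as the state of those still gradable.

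**Working it through.** **Is a removed rule likely?** SAP 5.4.1 to 5.5.6 each announce decision rules that are not visible in the public text. SAP 5.5.7 and 5.5.8 announce none and read as complete. A scoring rule removed from those two sections is therefore unlikely, although other blank sections (SAP 2.6, 5.6, 7.1) cannot be checked.

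**Figures in the plan.** None is visible for these endpoints, so there is nothing to reproduce. What follows is sensitivity arithmetic.

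**Inputs**
- From the documents: N = 108 (SAP 2.2); baseline category 2 to 5 (protocol 4.2).
- Assumed: k = 1 to 8 study-limb amputees, with everyone else measured; mean change in those measured m = -1.5 to -2.5 categories; share improved by at least one category p = 80%; worst category 6. The documents name only 2 to 5, so the top of the scale is an assumption. An amputee's change under worst-category scoring is then w = 6 - 5 = +1 to 6 - 2 = +4.

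**Mean change.** Measured-only gives m. Counting amputees at the worst category gives [(N - k)m + kw]/N. The difference is k(w - m)/N, where w - m runs from 1 + 1.5 = 2.5 to 4 + 2.5 = 6.5.

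**Share improved.** Counting amputees as not improved gives p(N - k)/N.

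| k | shift in mean (categories) | share improved (80.0% if measured only) |
|---|---|---|
| 1 | 2.5/108 to 6.5/108 = 0.02 to 0.06 | 79.3% |
| 3 | 7.5/108 to 19.5/108 = 0.07 to 0.18 | 77.8% |
| 5 | 12.5/108 to 32.5/108 = 0.12 to 0.30 | 76.3% |
| 8 | 20/108 to 52/108 = 0.19 to 0.48 | 74.1% |

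If only 80 other subjects were measured at a late visit, the denominator is 80 + k. The shift becomes 0.03 to 0.08 for k = 1 and 0.09 to 0.24 for k = 3.

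**Amputees graded 0 rather than worst.** The two means differ by 6k/108: 0.06 for k = 1 and 0.17 for k = 3.

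**Count of worsened subjects.** This row is small, so a few events show more clearly. With an assumed 3/80 worsened (3.8%), adding 2 to 4 amputees gives 5/82 = 6.1% to 7/84 = 8.3%, a ratio of 1.6 to 2.2. With an assumed 8/80 (10.0%), it gives 10/82 = 12.2% to 12/84 = 14.3%, a ratio of 1.2 to 1.4. The ratio depends on the base chosen.

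**ABI.** Assume a mean gain g of 0.20 to 0.30 and an amputee's change c of 0 or -0.6. The overstatement is k(g - c)/108: for k = 1, 0.20/108 to 0.90/108 = 0.002 to 0.008; for k = 3, 0.60/108 to 2.70/108 = 0.006 to 0.025.

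**Chance of no event.** At assumed amputation rates of 0.5%, 1% and 2%, the probability of none in 108 is 0.995^108 = 58%, 0.99^108 = 34% and 0.98^108 = 11%.

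**The case against.** A reader might infer that the plan drops amputees, or scores them as symptom-free, and so overstates improvement. The documents do not say that. Protocol 5.7 requires resting ABI/TBI and Rutherford classification at every scheduled visit and makes no exception after amputation, so a site might record nothing, a high category or a low one. A reader might also infer that ABI is always lost. A removal just above the metatarsals can leave the ankle, so the pressure is lost for certain only when the ankle is lost. These corrections stand.

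Limb loss is not hidden either. It is estimated by Kaplan-Meier with a 95% confidence interval at the same four time points, and adverse events are tabulated and listed. That stands too, but it does not change what the Rutherford table says about the subjects it omits.

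The unseen table specifications in SAP 7.1 may show not-assessed counts or full denominators. SAP section 7 makes enrolled subjects the default table population, and SAP 5.5.7 lists its statistics as a minimum. The finding is therefore confined to visible text.

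Finally, worst-category scoring changes the quantity measured from symptom status to symptom status combined with limb loss. That is a fair reason not to make it the main analysis. For deaths, a change score is undefined and the direction of any effect is unknown, so a separate row is enough.

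**Conclusion.** The point holds in a limited form. The available-case rule is written down for both endpoints and both populations, and no visible text says how study-limb amputation or death enters the summaries. Improvement may be overstated if amputations occur and the subjects are ungraded or graded as improved. A firm statement that it is overstated goes beyond the documents.

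On the assumed inputs, 1 to 3 amputees of 108 move the mean Rutherford change by about 0.02 to 0.18 category and the share improved by about 0.7 to 2.2 points from 80%. With 5 to 8 amputees the ranges are about 0.12 to 0.48 category and 3.7 to 5.9 points. With none, this source of bias is zero. Every range rests on assumed counts, mean change and top category.

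Severity is minor: these are descriptive secondary endpoints with no test, and neither primary endpoint is affected.

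**What to change.** - **SAP 5.5.8, main table.** Show the count of each Rutherford outcome at each visit over the ITT denominator, with study-limb major amputation, death and not assessed as separate rows. An amputee is then never counted as improved, whatever grade the site enters.
- **SAP 5.5.8, sensitivity analysis.** Repeat the change summary with study-limb major amputation scored as the worst category on the scale from that visit onward. State in the SAP what that category is, since the documents name only 2 to 5.
- **SAP 5.5.7.** Beside each mean, give the number of subjects without an ABI and the reason. Amputation, death, missed visit and ABI not measurable at entry (inclusion criterion 5 admits such subjects on TBI) should be distinguishable.

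The amputation, death and study-completion data are already collected, so the cost is SAP wording and a little table work. If amputations occur, the Rutherford summary will look slightly less favourable.

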5.5.9 Stent Fractures

All subjects from both the ITT and PP populations which have x-ray images assessable by the study core lab will be used to create a table displaying the counts of each fracture type at 12, 24 and 36 months. All values measured within the defined window will be used in tabulation.

CONFIDENTIAL INFORMATION

5.6 Additional Analysis

[figure not shown]
6 Analysis Specifications

6.2 Primary Endpoint

6.3 Verification Level for Statistical Output

7 Data Sets, Tables, Figures, and Listings

At a minimum, the following set of Tables, Figures, and Listings will be produced for the report. Unless specified, the populations for all tables are all of the “Enrolled Subjects”.

CONFIDENTIAL INFORMATION

MD133254 Statistical Analysis Plan Template
Revision#: 1
Doc Type: GC

7.1 Analysis Tables

CONFIDENTIAL INFORMATION

[figure not shown]
MD133254 Statistical Analysis Plan Template
Revision#: 1
Doc Type: GC

7.2 Analysis Listings

7.3 Analysis Figures

8 References

